1.3.3 Radiation Dosimetry

Table 1. The Lymphoseek radiation doses (mGy/MBq) to organs and tissues of an average patient (70 kg) with breast cancer or melanoma

Target Organ	Adults With Breast Cancer	Adults With Melanoma
brain	0.0002	0.0050
breast (injection site)	0.0897	0.0427
gall bladder wall	0.0019	0.0038
lower large intestine wall	0.0007	0.0031
small intestine	0.0005	0.0032
stomach	0.0010	0.0030
upper large intestine wall	0.0007	0.0031
kidney	0.0101	0.0150
liver	0.0018	0.0050
lungs	0.0020	0.0032
muscle	0.0005	0.0024
ovaries	0.0101	0.0162
red marrow	0.0007	0.0027
bone	0.0010	0.0047
spleen	0.0015	0.0032
testes	0.0027	0.0056
thymus	0.0063	0.0031
thyroid	0.0048	0.0025
urinary bladder	0.0032	0.0076
total body (blood) ^c	0.0011	0.0030
Effective Dose (males, mSv/MBq)	0.01600	0.01094
Effective Dose (females, mSv/MBq)	0.01785	0.01357

^a Calculated from data of 18 breast cancer patients who received four peritumoural injections of 4, 20, and 100 μg doses of Lymphoseek.

^b Calculated from data of 18 melanoma patients who received four intradermal injections of 20, 100, and 200 μg doses of Lymphoseek.

^c Blood represents total body exposure segregated from independent measurements of other organs and tissues.

1.3.4 Radiation Exposure

Participants in this study will be exposed to radiation during both scanning procedures. The SPECT/CT scan will expose the participant to approximately 6.1 millisieverts of radiation. The FDG PET/CT scan will expose the participants to approximately 13-15 millisieverts.

2 TRIAL OBJECTIVES

2.1 Primary Objective(s)

- Estimation of the concordance of Tc99m localization in liver metastases from colorectal carcinoma (CRC) using SPECT/CT imaging and abdominal FDG PET/CT imaging per subject.
- Evaluation of safety including monitoring the incidence of adverse events and changes over time in laboratory tests, vital signs, and physical examination findings.

2.2 Secondary Objective(s)

- Estimation of the optimal dose of Technetium Tc 99m tilmanocept
- Evaluation of other areas of localization of Technetium Tc 99m tilmanocept.

3 OVERVIEW OF METHODOLOGY AND DESIGN

3.1 Overall Trial Design

This is a single-center, open-label, within-subject feasibility study of tilmanocept in the localization of liver metastasis from CRC. Up to 6 subjects will receive a single IV dose of 50 µg tilmanocept radiolabeled with 2 mCi Tc 99m and imaged at 4-6 hours post-injection. Up to 6 subjects will receive a single IV dose of 200 µg tilmanocept radiolabeled with 2 mCi of Tc99m and imaged at 4-6 hours post-injection.

See [Appendix 1, Schedule of Events](#).

3.2 Justification for Study Design and Population

This study is designed to evaluate the safety and tolerability of a single dose of Tc 99m tilmanocept administered intravenously. SPECT/CT imaging of the subject's abdominal cavity (to include the liver) will be reviewed to establish concordance with images previously acquired with FDG PET/CT imaging.

This study is designed to evaluate the use of Tc 99m tilmanocept as an imaging agent in subjects with known active liver metastasis from CRC by comparing to FDG PET/CT images.

No clinical trials have been conducted to evaluate IV administration of Tc 99m tilmanocept performance in this population. The rationale for evaluating Tc 99m tilmanocept in this subject population is discussed in [Section 1.1](#) and [Section 1.2](#)

3.3 Protocol Adherence

Strict adherence to all specifications outlined in this protocol is required for all aspects of the study conduct; the investigator may not modify or alter the procedures described in this protocol. If protocol modifications are necessary, all alterations that are not solely of an administrative nature require a formal protocol amendment for the involvement of Institutional Review Board(s) (IRB(s)).

If an investigator has deviated from the protocol in order to eliminate an immediate hazard to subjects or for other inevitable medical reasons, the investigator shall document all such deviations, including the reasons thereof, and submit the document to the sponsor and the head of the medical institution as applicable.

3.4 Trial Duration

Subjects will be “on trial” for approximately 35 days.

4 STUDY POPULATION

The evaluation of tilmanocept in liver metastasis from CRC will involve up to 12 evaluable subjects.

4.1 Inclusion Criteria

Each subject must meet the following criteria to be enrolled in this study.

1. The subject has provided written informed consent with Health Information Portability and Accountability Act (HIPAA) authorization before the initiation of any study-related procedures;
2. The subject must be ≥ 18 years old;
3. The subject must have a diagnosis of adenocarcinoma of the colon and/or rectum with confirmed metastases to the liver
4. The subject must have an Eastern Cooperative Oncology Group (ECOG) performance status of 0-3;
5. The subject must be at least 4 weeks past any major intraabdominal surgery, including surgery to the liver;
6. Subjects with prior malignancies other than colon and/or rectal cancer are allowed, provided they have been treated with curative intent, and have no evidence of recurrence of that malignancy;
7. If of childbearing potential, the subject has a negative urine pregnancy test within 48 hours before administration of Tc 99m Tilmanocept, has been surgically sterilized, or has been postmenopausal for at least 1 year

4.2 Exclusion Criteria

Subjects who meet any of the following criteria will be excluded from the study.

1. The subject is pregnant or lactating;
2. The subject has undergone any liver surgery, exclusive of a biopsy;
3. The subject has known sensitivity to dextran;
4. The subject has had preoperative chemotherapy, immunotherapy, or radiation therapy within the 10 days prior to Tc 99m Tilmanocept administration;
5. Before the administration of Tc 99m Tilmanocept, has received any radiopharmaceutical within 7 radioactive half-lives of that radiopharmaceutical;
6. Has received an investigational product within the 30 days prior to Tc 99m Tilmanocept administration

4.3 Recruitment

Up to 12 evaluable subjects will be recruited from medical practice in accordance with the inclusion and exclusion criteria listed above. Potentially suitable subjects will be asked by the treating specialist about their willingness to participate in this trial. After 3 subjects have been enrolled into Cohort 1, the data will be reviewed by the PI and Navidea to determine if additional subjects should be enrolled and if additional timepoints should be considered. If it is determined that additional enrollment will not provide meaningful data, enrollment into Cohort 2 will begin. After 3 subjects have been enrolled into Cohort 2, the data will be reviewed by the PI and Navidea to determine if additional subjects should be enrolled and if additional timepoints should be considered.

4.4 Withdrawal

In accordance with the Declaration of Helsinki, each subject is free to withdraw from the trial at any time and without providing a reason.

Should a subject withdraw after administration of the IP, all efforts will be made to complete and report the observations up to the time of withdrawal as thoroughly as possible.

The investigator may withdraw a subject from the trial at any time at the discretion of the investigator for any of the following reasons:

- A protocol violation occurs
- A serious or intolerable AE occurs
- A clinically significant change in a laboratory parameter occurs
- At the investigator's/sponsor's discretion as long as it is in the best interest of the subject
- The sponsor or investigator terminates the study
- The subject requests to be discontinued from the study

4.5 Enrollment and Screen Failures

Subjects who sign an informed consent form (ICF) but are ultimately not injected will be considered screen failures. Subjects will be assigned a subject identification number at the time the ICF is signed. A subject will be considered enrolled once injected with Technetium Tc 99m on Day 1. Demographic data and the reason for the screen failure will be collected for all screen failure subjects. Enrollment will continue until a total of up to 12 subjects have completed SPECT/CT imaging.

Subject Identification

After the subject provides written informed consent, the site will assign the subject a 7-digit subject number. Subject numbers are to be assigned in a sequential manner using the following format:

Digits 1 to 2: Trial number (e.g., "25")
Digits 3 to 4: Site number (e.g., "01")
Digits 5 to 7: Sequential subject number (e.g., "001", "002", "003")

For example, the first subject consented at site 01 is subject number "25-01-001."

Subjects will maintain the same number given at screening for the entire trial. If a subject is a screen failure, the number will not be used for any other subject.

5 INVESTIGATIONAL PRODUCT

5.1 Identification of Investigational Product

Tilmanocept is a radiotracer that accumulates in CD206-expressing tissue by binding to the CD206 mannose binding receptors that reside on the surface of dendritic cells and macrophages.

5.2 Investigational Product Dosage and Administration

Subjects will receive the administration of Tc 99m tilmanocept through an IV route of administration. Cohort 1 will receive an IV injection of 50 μ g tilmanocept radiolabeled with 2 mCi (74MBq) Tc99m in 1.0 mL from a single dose syringe. Cohort 2 will receive an IV injection of 200 μ g tilmanocept radiolabeled with 2mCi (74MBq) Tc 99m in 1.0mL from a single syringe. Tc 99m tilmanocept will be administered as a slow push through a catheter. At the completion of the injection, a 10 cc sterile normal saline flush will be administered. The preferred site of IV placement will be the left or right antecubital vein.

The final administered dose will be \pm 20% of the tilmanocept mass dose and radiolabel mCi dose assignment.

Dose levels administered in this study were based on the safety and imaging results of Navidea studies NAV3-21, “An Evaluation of the Safety of Escalating Doses of Tc 99m Tilmanocept by Intravenous (IV) Injection and Skeletal Joint Imaging with SPECT in Subjects with Active Rheumatoid Arthritis (RA) and Healthy Controls” and NAV3-23, “Evaluation of Subcutaneously (SC) Injected Tc 99m Tilmanocept Localization in Active Rheumatoid Arthritis (RA) Subjects by SPECT and SPECT/CT Imaging.” The safety and localization in this study is expected to be similar to the results collected in these studies.

5.3 Treatment Assignment

In this open-label, non-randomized, single center, study all subjects will receive either 50 μ g or 200 μ g tilmanocept radiolabeled with 2mCi (74MBq) Tc99m in 1.0mL. The clinical site will send a request to Navidea for subject cohort assignment. The Navidea project manager will confirm treatment group assignment and send authorization back to the investigator prior to placement of the dose order.

The investigator will receive the dose from the supporting Cardinal Health pharmacy.

5.4 Packaging and Labeling

Tilmanocept cartons ready for radiolabeling will be shipped and stored at the region-specific Cardinal Health radiopharmacy. Tilmanocept is provided in a vial. Vials are packaged as a kit. A carton contains five vials of tilmanocept. One kit, which is one tilmanocept vial, should be used for no more than one subject. The carton also contains five shield labels and 25 syringe labels. This package has been designed specifically for tilmanocept and protects the vials during shipment, handling, and storage. Navidea will provide a radiolabeling protocol and Quality Control worksheets. Cardinal Health will radiolabel tilmanocept with either 50 μ g or 200 μ g tilmanocept radiolabeled with 2mCi (74MBq) Tc99m in 1.0 mL and deliver one syringe to the clinical site radiopharmacy that is ready for administration.

The investigator (or designated personnel) will confirm receipt of the IP in writing and will use the IP only within the framework of this clinical study and in accordance with this study protocol. For each subject, he/she will keep a record of the IP dispensed and store all other forms that accompanied the delivery of the radiolabeled product to the clinical site. These documents are to be filed in the ISF. Overall drug accountability and reconciliation will be completed by the sponsor or its representative. A list of IP vials and other materials that were returned, or destroyed, must be recorded and signed by the PI or an appropriately qualified designee as documented in the study site responsibility sheet. An overall accountability and reconciliation form of the IP will be prepared and completed. If there are any discrepancies, they must be investigated and their resolution documented. All unused study kits will be destroyed in accordance with institutional destruction procedures.

6 THERAPIES OTHER THAN INVESTIGATIONAL PRODUCT

6.1 Prior and Concomitant Therapy

All medications taken 30 days prior to Tc 99m tilmanocept injection through the 5 ± 3 days post-injection safety follow-up will be documented. Subjects must not have chemotherapy, immunotherapy, or radiation therapy within the 10 days prior to Tc 99m Tilmanocept administration

6.2 Post-Study Therapy

There are no post-study therapy restrictions.

7 STUDY PROCEDURES

7.1 Screening Visit (Day -29 to Day 0)

- Obtain signed informed consent for study participation
- Preliminary review of inclusion and exclusion criteria
- Allocation of unique subject number; this number will be used to document the subject data in the case report form (CRF) and enrollment log
- Interview including the following subject-specific characteristics:
 - Demographic data
 - Medical/surgical history (including concomitant diseases)
 - Medication history
- Vital signs (body temperature, heart rate, blood pressure, and respiratory rate).
- Blood draw for routine hematology and chemistry
- Urine collection for routine urinalysis and for pregnancy testing for women of child-bearing potential. Females of child bearing potential are defined as women that are not surgically sterile (hysterectomy or bilateral oophorectomy) nor postmenopausal for at least 1 year prior to screening. Women who are not of childbearing potential will not require a pregnancy test.
- Physical examination including height and weight and a review of major body systems; any clinically relevant finding is to be documented as baseline finding.
- Subjects will undergo a FDG PET/CT scan to identify hepatic lesions.

7.2 Day 1 (Injection and Imaging Procedures)

7.2.1 Before Injection

- Assessment of AEs
- Concomitant medication review
- Final check of inclusion/exclusion criteria
- Vital signs (body temperature, heart rate, blood pressure, and respiratory rate) within 15 minutes

7.2.2 Injection of Tc 99m tilmanocept

Both cohorts will be injected from a single syringe in a single IV injection.

Table 2. Dose Cohort and Route of Administration Groups

Dosing Cohorts	
Cohort 1	Cohort 2
IV Injection 50µg tilmanocept in 1.0 mL 2 mCi Tc99m	IV Injection 200µg tilmanocept in 1.0 mL 2 mCi Tc99m
Up to 6 subjects	Up to 6 subjects

Up to 12 subjects may be injected and imaged, divided into 2 cohorts of up to 6 subjects each.

Cohort 1 subjects will receive a Tc 99m tilmanocept IV injection in 1.0 mL and 2 mCi injected as a slow push into a catheter. At the completion of the injection, a 10 cc sterile normal saline flush will be administered. The preferred site of IV placement will be the left or right antecubital vein.

Cohort 2 subjects will receive a Tc 99m tilmanocept IV injection in 1.0 mL and 2 mCi injected as a slow push into a catheter. At the completion of the injection, a 10 cc sterile normal saline flush will be administered. The preferred site of IV placement will be the left or right antecubital vein.

Injection and imaging will begin with Cohort 1. After 3 subjects have been enrolled into Cohort 1, the imaging and safety data will be reviewed by the site staff and Navidea personnel to determine if additional subjects should be enrolled. If it is determined that additional enrollment will not provide meaningful data, for example no metastatic liver lesions were visualized by Tc 99m tilmanocept for any of the subjects in the cohort, enrollment into Cohort 2 will begin. After 3 subjects have been enrolled into Cohort 2, the data will be reviewed by the site staff and Navidea personnel to determine if additional subjects should be enrolled.

7.2.3 Post-Injection

The following procedures will be completed at the specified timepoints:

- 15 Minutes Post-Injection
 - Vital signs will be obtained (body temperature, heart rate, blood pressure, and respiratory rate)
- 4-6 Hours Post-Injection
 - Assessment of AEs
 - SPECT/CT will be obtained in the abdominal region (to include entire liver)
- 5 ± 3 Days Post-Injection
 - Assessment of AEs
 - Vital signs (body temperature, heart rate, blood pressure, and respiratory rate, after at least 5 minutes in a resting position)
 - Physical examination including a review of major body systems; any clinically relevant changes from screening are to be documented
 - Blood draw for routine hematology and chemistry
 - Urine collection for routine urinalysis

7.2.4 Imaging and Acquisition of Imaging Data

The camera used to obtain the images should be a 2 or 3-headed SPECT/CT camera equipped with a low-energy, high-resolution collimator with a 15% window (20% can be used if 15% setting not available) centered over a 140keV peak.

The camera must have passed the daily SPECT QC tests as per the manufacturer's recommendation for that day's scan schedule.

Whenever possible subject should be asked to void after injection and prior to the first imaging session and again between imaging sessions.

Image acquisition of subjects in this study will be via SPECT/CT at 4-6 hours post-injection. The abdominal regional will be imaged and will include the entire liver.

7.2.5 Image Acquisition

The investigator will document the manufacturer and type of the SPECT or SPECT/CT scanner used in both the subject's file and CRF. The same scanner should be used during the entire course of the study and any updates to hardware or software should be avoided. If changes occur, they must be reported to the sponsor.

The manufacturer's standard SPECT acquisition parameters for Hepatobiliary SPECT (HIDA SPECT) should be followed. This would typically result in a total acquisition time of 30 ± 10 minutes. For SPECT/CT cameras; the CT scan should be set for "low-dose" mode to obtain and use the transmission scan for attenuation correction. For non-CT coupled SPECT cameras, attenuation correction would be applied using standard ellipse-based Chang methods. Regardless of the number of heads on the SPECT camera, the emission data should be acquired with each camera head orbiting the full 360° around the patient with typically 90-120 projection views per head.

7.2.6 Evaluation of SPECT/CT Images

Tilmanocept localization in subjects with liver metastasis from a CRC will be evaluated through SPECT/CT image analysis by the onsite Nuclear Medicine physician. First, a "routine clinical" assessment of the overall technical adequacy of the scan will be made. It is anticipated that this would be done by viewing the projection data cine (allowing for an initial visual assessment of patient motion during the acquisition). This would be followed by a visual evaluation of the transverse reconstructed slices of the liver to assess whether hotspots could be attributed to expected metastases sites. The clinician reading the transverse SPECT liver slices will have access to the previously conducted PET scans and will report any concordance between uptake of tilmanocept with FDG at the metastases sites. The number of sites of concordance (between SPECT and PET) as well as the total number of diagnosed metastases sites for each subject imaged will be reported to the sponsor. Following the technical assessment, an overall assessment of the scan will be made. A de-identified copy of the Nuclear Medicine scan report will be provided by the site to the sponsor. For each subject the SPECT/CT scans and FDG PET/CT scans (in Digital Imaging Communications in Medicine [DICOM] format) will be forwarded to the sponsor.

All regions of interest (ROIs), standardized uptake values (SUVs), and quantitative analyses will be done by the sponsor.

Given that the imaging site has electronic transfer capabilities, each subject's scans will be transferred to the sponsors data server. If such an e-transfer is not possible, a standard "patient CD disc" will be generated and sent to the sponsor via ground mail.

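### The SPECT/CT reader has the FDG PET scans available and reports concordance, with no PET-closed or locked first read, so the Section 9 concordance endpoints are not protected from comparator knowledge

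*Combined protocol and SAP*

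**What the plan says.** Section 7.2.6 gives the visual evaluation to one role, the on-site nuclear medicine physician. After a technical check, the liver slices are viewed "to assess whether hotspots could be attributed to expected metastases sites". On the comparator, the section says: "The clinician reading the transverse SPECT liver slices will have access to the previously conducted PET scans". That clinician also reports the concordance.

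The counts named for transmission to the sponsor are: "The number of sites of concordance (between SPECT and PET) as well as the total number of diagnosed metastases sites". In addition, "A de-identified copy of the Nuclear Medicine scan report will be provided by the site to the sponsor", and both image sets go to the sponsor, which performs the region-of-interest, SUV and quantitative work.

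Section 3.2 says that the SPECT/CT "will be reviewed to establish concordance with images previously acquired with FDG PET/CT imaging". Section 9 defines concordance in both directions, per subject (at least one shared liver lesion) and per lesion (tilmanocept lesions also seen on FDG PET/CT, and the reverse). The Synopsis makes per-subject concordance a primary endpoint and the two per-lesion measures secondary. It describes all analyses as descriptive and intended to help design a larger study.

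**The concern.** A two-way concordance percentage is easiest to interpret when each modality's lesions are called in their own right and then compared. Here the person calling foci on SPECT/CT may look at the PET, is asked about sites where metastases are expected, and decides what counts as concordant. A doubtful focus at a site known from PET can be accepted more readily than the same focus elsewhere. The reported figure could then mix what tilmanocept SPECT/CT shows unaided with what it shows once the reader knows where to look.

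A larger study would need to know which of the two it is planning on. The same reads may also reach the review after 3 subjects in each cohort. Section 7.2.2 says that "the imaging and safety data will be reviewed by the site staff" and sponsor personnel, but not which reads are used.

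**Working it through.** The plan gives no power, precision or expected-concordance figure to reproduce. Its only sample-size arithmetic is 2 cohorts × 6 = 12, which is consistent. The check is therefore mainly a comparison of passages.

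1. **Is there a protected read anywhere?** Section 7.2.6 sets no order between calling foci and opening the PET, no lock and no second reader. The sponsor's stated image work is quantitative; no masked lesion read is described. Sections 3.2, 7.2.2 and 9 add none. The plan does not say who reads the FDG PET/CT, so the SPECT reader may already know it.

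2. **Which endpoints depend on this read?** All four Section 9 concordance measures. The per-subject measure needs only one shared lesion, so a single focus called with PET help can make a subject concordant.

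3. **Which way would bias run?** Let C be concordant foci, S SPECT-only foci and P PET lesions.
   - Accepting a doubtful focus at a PET site raises C, and with it C/P and C/(C+S).
   - Dismissing a doubtful focus away from any PET site lowers S, and so raises C/(C+S).
   - PET could also lead the reader to reject a focus that would otherwise have been matched, which lowers C.

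   The first two effects seem more likely, so upward bias is a reasonable inference. No input in the documents fixes the direction or gives a size.

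4. **Do the listed counts support Section 9?** Take the total diagnosed sites to be the PET lesions, P (an assumption; the term is not defined). PET-to-tilmanocept concordance is C/P, which the two listed counts determine. Tilmanocept-to-PET concordance is C/(C+S), and S is not listed. With assumed C = 6 and P = 10, C/P = 60% throughout, while C/(C+S) varies:
   - S = 0: 6/6 = 100%
   - S = 2: 6/8 = 75%
   - S = 4: 6/10 = 60%
   - S = 8: 6/14 = 43%

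   If the total meant all sites on either modality, it would still not separate PET-only from SPECT-only. These values show only that the listed counts do not determine the percentage. They are not an estimate of bias.

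5. **What could it do to the cohort reviews?** Section 7.2.2's example for moving on from Cohort 1 is that no liver metastasis was visualized in any subject. If a PET-aided call led to continued enrollment, the effect is at most 6 − 3 = 3 further subjects in a cohort.

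**The case against.** The strongest reply is that PET access is deliberate and suits the aim. Section 3.1 describes a within-subject feasibility study, and eligibility requires known disease: "The subject must have a diagnosis of adenocarcinoma of the colon and/or rectum with confirmed metastases to the liver". Whether the tracer reaches known lesions is a fair question for a PET-informed read, and matching cannot be done without the PET. There is no hypothesis test or performance claim to invalidate. This stands, and it is why the PET-informed result should be kept.

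Four stronger readings are tempting but not supported:

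- A reader might infer that the PET is open when hotspots are first called. The text grants access and is silent on timing; it permits this but does not state it.
- A reader might infer that unaided SPECT calls can never be separated from aided ones. Both DICOM sets go to the sponsor for every subject, so a PET-closed re-read remains possible. It is simply not required.
- A reader might infer that the plan needs no SPECT-only count. Section 9 implies one, and the scan report, images or CRF may supply it. The gap is that Section 7.2.6 does not list it.
- A reader might take the weight of one subject (1/12 = 8.3 points, 1/6 = 16.7, 1/3 = 33.3, if all imaged subjects form the denominator) as the size of the problem. Those figures hold for any binary endpoint at these numbers, masked or not, and say nothing about bias.

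What remains is that Section 9 reports lesions found by each modality in both directions, and the results feed a later design, while no required read shows what SPECT/CT finds before the PET is consulted.

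**Conclusion.** The point holds as a gap in protection, not as a demonstrated bias. As written, the plan leaves primary per-subject and secondary per-lesion concordance open to comparator knowledge. The size is unknown, and an upward direction is inference that rests on how readers tend to treat doubtful foci. The exploratory status limits the consequence, and any effect through a cohort review is bounded at 3 additional subjects per cohort. The unlisted SPECT-only count is a secondary matter of aligning Section 7.2.6 with Section 9. The change is inexpensive and is best made before reading starts, because a later re-read by a physician who has seen the PET would be less well protected.

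**What to change.** Rewrite Section 7.2.6 as a two-step read by the existing on-site physician.

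- **Step 1.** With the PET images and report closed, record and lock on the CRF the number and location of every hepatic focus on SPECT/CT, and whether this reader had already seen the subject's PET.
- **Step 2.** Open the PET and match lesion by lesion under a pre-written, one-to-one location rule. The rule should not depend on CT overlap alone, because Section 7.2.5 also provides for cameras without CT: "For non-CT coupled SPECT cameras, attenuation correction would be applied using standard ellipse-based Chang methods". Report concordant, SPECT-only and PET-only counts to the sponsor, and define the total number of diagnosed sites.

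In Section 9, report the concordance endpoints side by side from the locked read and from the PET-informed read, and state in advance which is primary. Give both to the 3-subject reviews.

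The cost is protocol and CRF wording and slightly more reading time, with no extra scan or reader. Concordance may be lower in the locked read. Masking is only partial: the same physician may have read the PET, and every subject is known to have liver metastases. Step 1 therefore protects the number and location of foci, not the knowledge that disease is present. Reader status should be reported with the result.
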